**Notes for Tables 5 and 6:**

1. Follow-up visit will occur 28 days after the End of Study visit in Part B of the study.
2. A complete physical exam will be performed at Screening and Baseline visits. A modified physical exam including the patient's lungs and cardiovascular body systems will be performed at all other visits. For Safety Visits, only chest and skin exam are required.
3. Height is collected at the Screening visit only.
4. Blood samples for laboratory tests include: Chemistry (including AST and ALT), Hematology and Biomarkers (Blood samples for biomarkers will not be collected at Screening.) For Safety Visits, only AST and ALT are required.
5. Females of childbearing potential are required to take a urinary pregnancy test at each visit except the Follow-up visit.
6. Patients that pass screening and are scheduled to be randomized will receive a LCM to be worn for 24 hours and returned to the site at the Baseline visit. LCM will be worn for 24 hours at Visits 5 and 8. A paper diary will also be dispensed to the patient to record activities during the 24-hour period.
7. HRCT scans will be performed at Visits 2 and 8. The Baseline HRCT may be skipped if the HRCT for eligibility was performed less than 1 month prior to the Baseline visit.
8. Study material dispensation will occur at Visit 8 for those patients participating in Part B of the study.
9. Patients will be assessed for eligibility to participate in AP01-005 at EOS/Visit 12. Those enrolling in AP01-005 will use EOS/Visit 12 as their AP01-005 Baseline visit.
10. Patients enrolling in AP01-005 will not participate in the Follow-up visit.
11. Patients awaiting site approval of AP01-005 only.

Avalyn Pharma, Inc.  
AP01-002

Protocol V2.1  

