### **7.4.6. Laboratory Assessments for Hematology, Serum Chemistry, Biomarkers and Urinalysis**

At each visit, clinical laboratory tests will be conducted at the study's central laboratory with the exception of biomarkers, which may be sent to a specialty lab. Clinical laboratory tests will include:

- Hematology: complete blood count with differential, platelet count
- Serum Biochemistry: bilirubin, alkaline phosphatase, sodium, potassium, chloride, bicarbonate, urea, creatinine, total protein, albumin, glucose, ALT, AST
- Urinalysis: pH, specific gravity, presence/absence of protein, glucose, blood
- Biomarkers: CXCL13, CCL18, MMP3 (progression-related) will be tested at Baseline only. CA19-9 and CA-125 (predictive of alveolar epithelial damage) will be collected at all visits except for the Screening visit.)

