## 11.5 Efficacy and Safety Analyses

### 11.5.1 Efficacy Analyses

The following analyses will be performed:

- Change from Baseline in absolute FVC % predicted
- Change from Baseline in cough frequency as measured by LCM
- Change from Baseline in the total KBILD score and in KBILD breathlessness and activity domains
- Change from Baseline in the total LCQ score.
- Change from Baseline in cough severity as measured by VAS
- Change from Baseline in extent of fibrosis and lung volumes as assessed by HRCT
- Change from Baseline in  $D_{LCO}$

The primary endpoint of interest for efficacy is the absolute change from Baseline to Week 24 in FVC % predicted. Linear mixed-effects modeling will be used and differences between treatment arms will be examined. Baseline FVC, region and progression-related biomarker (CXCL13, CCL18, MMP3) values will be considered as covariates in the model. Further details on the assumptions and planned analyses will be provided in the SAP. Similar modeling strategies will be employed for longer term data obtained from Part B of the study. No control group is included in this study, however exploratory analyses will be conducted using registry and historical data as comparators. Details of all analyses will be provided in the SAP.

In order to assess the impact of treatment on cough in those patients for whom coughing is of greatest concern, additional analyses of cough frequency will be performed on the subset of patients with baseline cough severity VAS > 40 millimeters and in patients with baseline cough frequency  $\geq 10$  coughs/hour during awake hours.

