8.1. Primary Efficacy Endpoint and Analysis

Spirometry will be conducted at approximately the same time each visit (within 60 minutes of Day 1 spirometry measurement) with the patient in seated position. The test will be performed to American Thoracic Society/European Respiratory Society (ATS/ERS) guidelines³. On days of clinic visits (including the screening visit), patients must refrain from strenuous activity at least 12 hours prior to pulmonary function testing (PFT). FVC % predicted will be calculated using the ERS Global Lung Function Initiative 2012 equations² as outlined in the clinical study manual.

PFTs will be collected at Screening, Baseline and at each post-Baseline time point (Week 4, 8, 12, 16, 20, 24, 36, 48, 60, 72 and Follow-Up) as described in Section 6.1.

The primary efficacy endpoint is the change from baseline in absolute FVC % predicted from Baseline to Week 24. The population used for efficacy analyses of the primary variable will be the PP with the FAS used for the first sensitivity analyses.

A linear mixed-effects model (PROC MIXED) will be used and differences between treatment groups between slopes estimating the change from baseline in absolute FVC % predicted from Baseline to Week 24 will be examined. Baseline FVC % predicted, region, age at screening, sex, baseline DL_{CO} % predicted, and baseline progression-related biomarker (CXCL13, CCL18, MMP3) values each categorized as >Median level vs. ≤Median level will be included as covariates in the model. This analysis requires at least three post-baseline FVC % predicted values in addition to baseline be available for a patient to be included in the analysis so that the slope estimated is identifiable. Similar modeling strategies will be employed for longer-term data obtained from Part B of the study. Spirometry data collected after patients switched dosing regimen from 50 mg once daily to 100 mg twice daily will be omitted for this analysis.

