and when complete, mail the LCM and diary back using the mailing materials provided. Further details regarding LCM dispensation and return will be outlined in the clinical study manual.

The following statistics for cough frequency (coughs/hour) as measured by LCM will be calculated and summarized separately for 24 hours and for awake time by treatment group and displayed in a table:

- Summary statistics of the cough frequency (coughs/hour) as measured by LCM at Baseline and at Visits 5 and 8 (Week 12 and 24)
- Summary statistics of the cough frequency (coughs/hour) as measured by LCM reflecting the absolute change from Baseline to Visit 5 and 8 (Week 12 and 24).

The following plot will be produced for cough frequency (coughs/hour) as measured by LCM:

- Mean Cough Frequency (coughs/hour) as measured by LCM Change from Baseline (\pm SD) vs. Visit Week (Week 12, Week 24) with lines for each treatment group.

A linear mixed-effect model (PROC MIXED) will be used and differences between treatment groups between the change from Baseline in coughs/hour as measured by LCM to Weeks 12 and 24 will be examined. Baseline cough frequency (coughs/hour), region, age at screening, sex, baseline D_{LCO} % predicted, and baseline progression-related biomarker (CXCL13, CCL18, MMP3) values each categorized as >Median level vs. \leq Median level will be included as covariates in the model. The model will include a random effect for patient and fixed effects for treatment, visit (Week 12 or Week 24), and the interaction between treatment and visit. To account for correlated repeated measures within patients a compound symmetric variance-covariance matrix will be used.

In order to assess the impact of treatment on cough in those patients for whom coughing is of greatest concern, additional analyses of cough frequency will be performed on the subset of patients with baseline cough severity VAS \geq 40 millimeters and in patients with baseline cough frequency \geq 10 awake time coughs/hour. When examining these subgroups, the outcome will be % change from baseline.

All data for LCM will be presented in a listing.

8.2.2. Change from baseline in the total KBILD score and in the KBILD breathlessness and activity domain score

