The following plot will be produced for extent of fibrosis and lung volumes as assessment by HCRT:

This document is confidential.

SAP Version: 3.0 (15JUL2021)
Controlled Document ID: **3903A.01**, Effective Date 29-Oct-2018
Filing requirements: TMF

Page 35 of 52

Statistical Analysis PlanSponsor: Avalyn Pharma, Inc.; Protocol No.: AP01-002

- Mean Extent of Fibrosis (or Lung Volume) Change from Baseline (\pm SD) vs. Weeks from Baseline (calculated based on visit date) for each lung region with lines for each treatment group.

A linear model will be used and differences between treatment groups between the change from baseline in whole lung extent of fibrosis and whole lung volume from Baseline to post-Baseline will be examined. Change from baseline will be the dependent variable and baseline whole lung extent of fibrosis (or whole lung volume), region, age at screening, sex, baseline D_{LCO} % predicted and baseline progression-related biomarker (CXCL13, CCL18, MMP3) values each categorized as $>$ Median level vs. \leq Median level, and time of HRCT (relative to baseline) will be included as covariates in the model.

All HRCT scan data will be presented in a listing including early termination and unscheduled visits.

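### Three biomarkers measured once are mandatory median-split covariates in the primary FVC, cough-frequency and HRCT models, and no rule covers a missing assay

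*SAP*

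**What the plan says.** Protocol 11.5.1 leaves the role of the biomarkers open: "progression-related biomarker (CXCL13, CCL18, MMP3) values will be considered as covariates in the model". It names no cut-point and refers details to the SAP.

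The SAP makes them fixed terms. In SAP 8 and 8.1, the primary FVC model, the three markers appear with baseline FVC % predicted, region, age, sex and baseline DLCO % predicted, and "values each categorized as >Median level vs. ≤Median level will be included as covariates in the model". SAP 8.2.1 uses the same set for Leicester Cough Monitor frequency, starting from "Baseline cough frequency (coughs/hour), region, age at screening, sex". SAP 8.2.5 does so for the HRCT linear model, starting from "baseline whole lung extent of fibrosis (or whole lung volume), region, age at screening, sex" and ending "and time of HRCT (relative to baseline) will be included as covariates in the model". SAP 8.1 extends similar modelling to Part B. SAP 12 lists only the added Full Analysis Set as a change from the protocol.

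On sampling, Protocol 7.4.6 says "CXCL13, CCL18, MMP3 (progression-related) will be tested at Baseline only", and the notes to Protocol Tables 5 and 6 say "Blood samples for biomarkers will not be collected at Screening". Protocol 7.4.6 also allows biomarker samples to go to a specialty laboratory.

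On missing data, SAP 6.3 covers summary tables and partial dates and points to SAP 8.1. The strategies in 8.1 impute in-clinic FVC only. Neither section mentions a missing baseline covariate.

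**The concern.** There are two issues, and the first carries more weight.

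**Missing assays.** A mandatory covariate with one sampling occasion and no fallback becomes a condition for entering the model. PROC MIXED, which the SAP names for FVC and cough frequency, omits records with a missing covariate unless told otherwise, as does an ordinary linear model. These covariates do not change over time, so one failed assay removes every record of that patient. The Full Analysis Set run does not help: it starts from all randomised patients, but the same covariates drop the same people, including those whose FVC has just been imputed after death or early termination. The data would already be thinned by the per-protocol exclusions in SAP 5.3 and the three-post-baseline-values requirement in SAP 8.1. The same silence permits another error: a derivation that tests whether a value exceeds the median could place a missing value in the low group unnoticed.

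**Median split.** Cutting a continuous marker at its median discards information if its effect is graded. A covariate included for precision then gives less of it.

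The arm comparison guides dosing for later studies (Protocol 2), so it should not depend on whether a single assay succeeded.

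**Working it through.** **1. Reproduce the plan's figure.** Inputs from Protocol 11.1: SD 4.5, 50 per arm, two-sided 95% interval. Half-width = 1.96 × 4.5/√50 = 1.247, the stated 1.25. This is an unadjusted within-arm figure and serves here only as a yardstick for lost patients.

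**2. Patients lost by default.** Let q be the missing rate per assay. The documents give none, so 3% and 5% are assumptions. If the whole sample fails, n = 50(1 − q). If the three assays fail independently, n = 50(1 − q)³.

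| q | Pattern | Lost | n per arm | Half-width |
|---|---|---|---|---|
| 3% | whole sample | 3.0% | 48.5 | 1.27 |
| 5% | whole sample | 5.0% | 47.5 | 1.28 |
| 3% | independent | 8.7% | 45.6 | 1.31 |
| 5% | independent | 14.3% | 42.9 | 1.35 |

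Protocol 11.1 also claims around 75% power between arms without stating the effect size. Assuming the cited oral trial's active-placebo gap, 3.9 − 1.5 = 2.4 points, 50 per arm gives 76%. Power falls to 74-75% with whole-sample failure and 70-72% with independent failure.

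**3. Information lost by the split.** For a normal covariate (here the log of the marker) with a linear effect, a median split keeps 2/π = 0.637 of the explained variance and loses 1 − 0.637 = 36%. Other assumptions give other answers:

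- Three markers with equal effects: joint loss about 36% if uncorrelated, 27% at correlation 0.3 and 23% at 0.6.
- Effect linear in a raw log-normal value (log-SD 0.25 to 1.0): 40% to 73%.
- True effect a step at the median: no loss.

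**4. Cost in the cough and HRCT models.** With R² the share of outcome variance that the continuous markers would explain (assumed), the ratio of standard errors, split to continuous, is √[(1 − 0.637R²)/(1 − R²)]:

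- R² = 5%: √(0.968/0.95) = 1.010
- R² = 10%: √(0.936/0.90) = 1.020
- R² = 20%: √(0.873/0.80) = 1.044

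Correlated markers give slightly less (1.028 at R² = 20% and correlation 0.6). The cost is therefore about 1-4%.

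**5. Cost in the primary model.** SAP 8.1 compares slopes between arms and lists no covariate-by-time terms. A covariate that is constant within a patient and enters as a main effect shifts level, not slope. With 100 patients, six visits, a random intercept and slope, and assumed variances, the generalised least-squares standard error of treatment-by-time was 1.074 with no covariates, with continuous covariates and with median splits, at R² of both 10% and 30%. The value 1.074 depends on the assumed variances. The equality does not when visits are complete, and it remains very close with some visits missing.

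**The case against.** The strongest reply is that fixing covariates in advance is the task the protocol gives the SAP, so moving from possible to mandatory terms is no fault. Prespecified splits also match the planned subgroups in SAP 6.6 and avoid assuming linearity. Both points stand. If the truth is a step at the median, the split is the better form and a linear term keeps only 64% of the explained variance.

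Deletion is also an inference. A reader might conclude that the plan orders patients with a missing assay to be removed; it does not. It is silent, and dropping them is the software default. The three assays belong to one Baseline blood collection, so whole-sample failure, the milder case, is the more plausible.

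Not every efficacy result is exposed. The longitudinal FVC model later in SAP 8.1 and the DLCO model in SAP 8.2.6 list no biomarkers, and the descriptive summaries do not need them. The Full Analysis Set itself does not shrink; only the usable records in the affected models do.

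Finally, a reader might take the categorising clause to cover baseline FVC, age and DLCO, or baseline cough and fibrosis. Region and sex sit in the same list and cannot be cut at a median, so the clause most naturally attaches to the biomarkers alone. The wording should be clarified, but no loss should be counted for the other covariates.

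**Conclusion.** The gap is real and modest in size. Three markers measured once are required terms in the primary FVC, cough-frequency and HRCT models, and nothing says what happens when one is missing. The larger potential cost is lost patients: 3-5% or 9-14% at an assumed 3-5% missing per assay, depending on whether failures occur together or independently. The true rate cannot be taken from the documents.

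The split is the smaller matter. A reader might infer that about a third of the precision is lost. The 36% applies to each marker's explained variance, and only for a linear effect on the log scale. In the cough and HRCT models it amounts to about 1-4% in standard error for an assumed R² up to 20%. In the primary slope contrast as written it is essentially zero. The split does not bias the randomised comparison.

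In a Phase 1b estimation study whose primary objective is safety, this is an inexpensive improvement, not a threat to validity.

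**What to change.** In SAP 8, 8.1, 8.2.1 and 8.2.5:

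- Enter CXCL13, CCL18 and MMP3 as continuous log-transformed terms, and keep median splits for the subgroup tables only.
- State that the baseline outcome, age and DLCO % predicted are continuous, which settles the scope of the categorising clause.
- Add one sentence on missing baseline covariates: replace a missing value by the mean of both arms pooled, or use a missing indicator, without using outcome or arm, so that no patient with outcome data is dropped.

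The third item protects all three models. The first brings its gain mainly in 8.2.1 and 8.2.5. The cost is SAP wording with no new data; the downside is a mild assumption of linearity on the log scale.

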#### **5.6. Patient Withdrawal Criteria**

Patient participation in the study is purely voluntary; patients can withdraw consent at any time for any reason without effect on subsequent care. This is an open-label study in which the investigator is aware of the patient's treatment assignment. The investigator, in consultation with the Medical Monitor, or the Medical Monitor may exercise his or her medical judgment to terminate a patient's participation in the study due to clinically significant changes in any clinical or laboratory parameter. If in the opinion of the investigator, the patient is failing the study drug for lack of efficacy, as evidenced by an excessive decline of FVC, during Part A of the study, the patient can be withdrawn and placed on alternative therapies. During Part B of the study, the investigator may choose to add nintedanib, but not oral pirfenidone, to the patient's treatment regimen.

Any randomized patient desiring to discontinue prior to study completion should be encouraged to discuss his or her reasons and concerns with the investigator. If, after discussion, the patient still chooses to discontinue participation in the study, the patient should be encouraged to attend an Early Termination visit. (Patients that discontinue during the screening process will be considered screen failures.) Patients who are discontinued during a scheduled visit will be encouraged to complete all unique assessments for both that study visit and the End of Treatment visit at the time of discontinuation. If a patient is still participating in Part A and has had a HRCT scan within the past month, the HRCT from the End of Treatment visit will not be performed.

An End of Study case report form (CRF) page will be completed for every patient who receives study medication whether or not the patient completes the study. The reason for any early discontinuation from the study will be indicated on this form. The primary reason for any early termination will be selected from the following standard categories:

- Adverse Event: Clinical or laboratory events occurred that in the medical judgment of the investigator, in consultation with the Medical Monitor and Avalyn Pharma, represents an unacceptable risk to the patient if he/she continues in the study. This includes serious and non-serious AEs regardless of relationship to study medication. The investigator must follow the patient until the AE resolves or satisfactorily stabilizes

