5.3. Per Protocol Set

The Per-Protocol Set (PP) will include all patients who were administered at least one dose of study medication, who have sufficient data to assess the primary efficacy endpoint, and who have no Major Protocol deviations that would impact the ability to appropriately assess the primary endpoint. Patients will be analyzed according to randomized treatment. Criteria for exclusion from the PP includes the following Major Protocol deviations:

- Violation of Inclusion/Exclusion Criteria
- Informed Consent not provided
- Study Drug Deviation
- Concomitant Medicine Restrictions

Summaries of all efficacy endpoints will be created using the PP.

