The primary endpoint of interest for efficacy is the absolute change from Baseline to Week 24 in FVC % predicted. Linear mixed-effects models will be used to estimate slopes representing the mean change from Baseline to Week 24 in each treatment group, and the difference between treatment groups will be examined. Baseline FVC % predicted, region, age at screening, sex, baseline D_{LCO} % predicted, and baseline progression-related biomarker (CXCL13, CCL18, MMP3) values each categorized as >Median level vs. ≤Median level will be included as covariates in the model. Similar modeling strategies will be employed for longer-term data obtained from Part B of the study.

No control group is included in this study; however, there is ample data in the literature showing a consistent rate of decline in IPF patients not receiving anti-fibrotic therapies. Historical data from the placebo groups of the three Phase III clinical trials of oral pirfenidone (ASCEND and CAPACITY trials) showed an average decline in FVC % predicted of ~4% at 6 months. These results will be used as a historical comparator. For each AP01 treatment group, a one sample Wald test will test H_0 : mean change from Baseline to Week 24 in FVC % predicted $\leq -4\%$ vs H_1 : mean change from Baseline to Week 24 in FVC % predicted $> -4\%$. For each AP01 treatment group, a 95% one-sided confidence interval will be derived for the difference (between A01 and historical reference) in the mean change from Baseline to Week 24 in FVC % predicted. Additionally, we will compare the change from baseline in FVC % predicted at Week 24 for each treatment group to the average decline in FVC % predicted at 24 weeks for patients with no documented antifibrotic treatment calculated from a set of (1) Pulmonary Fibrosis Foundation (PFF) Registry patients and (2) Australian IPF Registry patients, with matching baseline characteristics. For each treatment group and each registry, a two-sided Wald test will test: H_0 : 24-week $FVC\ decline_{AP01\ group} = 24\text{-week}\ FVC\ decline_{registry}$ vs. H_1 : 24-week $FVC\ decline_{AP01\ group} \neq 24\text{-week}\ FVC\ decline_{registry}$. For each of the 2 AP01 treatment groups and for each of the 2 registries, a 95% two-sided confidence interval will be derived for the difference (between AP01 and registry) in the mean change from Baseline to Week 24 in FVC % predicted.

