The primary population used for efficacy analyses will be the PP with the FAS used for specified sensitivity analyses.

This document is confidential.

SAP Version: 3.0 (15JUL2021)
Controlled Document ID: **3903A.01**, Effective Date 29-Oct-2018
Filing requirements: TMF

Page 30 of 52

Statistical Analysis PlanSponsor: Avalyn Pharma, Inc.; Protocol No.: AP01-002

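### The three-value minimum in the primary FVC slope analysis is not needed for identifiability, and it can understate decline in the single-arm comparisons

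*SAP*

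**What the plan says.** SAP section 8 (Efficacy) sets the model: "Linear mixed-effects models will be used to estimate slopes representing the mean change from Baseline to Week 24 in each treatment group". SAP 8.1 adds that this analysis "requires at least three post-baseline FVC % predicted values in addition to baseline be available for a patient to be included in the analysis" and gives one reason: "so that the slope estimated is identifiable".

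On the population, SAP 8.1 states: "The population used for efficacy analyses of the primary variable will be the PP with the FAS used for the first sensitivity analyses". SAP 5.3 admits to the per-protocol (PP) set only patients "who have sufficient data to assess the primary efficacy endpoint" and does not define sufficient. Protocol 11.3 already specifies PP for efficacy. The three-value minimum, by contrast, is not in Protocol 11.3 or 11.5.1, and SAP section 12 does not list it as a change from the protocol.

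Part A clinic spirometry is four-weekly, from Week 4 to Week 24. Protocol 5.6 allows withdrawal in Part A when the investigator judges that "the patient is failing the study drug for lack of efficacy, as evidenced by an excessive decline of FVC". Protocol 5.3 and 8.9.1 call for discontinuation if a patient needs oral pirfenidone or nintedanib during Part A.

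SAP section 8 then compares each arm's mean 24-week change with -4% (one-sided) and with two registries (two-sided).

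**The concern.** If the stated reason is wrong, the rule only discards usable data. The loss need not be neutral. A patient who leaves before the third value contributes nothing, and the protocol names falling FVC as a reason for leaving. If early leavers decline faster, the patients who remain show a milder average decline than the arm as a whole.

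The study has no control arm, so any statement of benefit against untreated decline rests on each arm's absolute change. That is where a shift towards zero does most harm.

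**Working it through.** **1. The plan's precision figure.** SAP 3.5 gives SD 4.5 and 50 patients per group. The half-width is 1.96 × 4.5 / √50 = 1.247, which reproduces the stated 1.25.

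**2. Identifiability.** The arm slope is a fixed effect estimated across patients. Baseline plus one later value already gives two time points.
- A random-intercept, random-slope model was fitted to 100 simulated patients, 30 of whom had only one or two post-baseline values. It converged and estimated every fixed slope and variance.
- Those 30 patients alone, with a random intercept, still gave a slope: -2.95, standard error 2.57. It is imprecise, but identified.
- The SAP's later in-clinic FVC model in 8.1 and its home-spirometry model in 9.2 use random patient and time effects and state no minimum.

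**3. Who is lost.** The third scheduled value is at Week 12. SAP 6.4 maps an early termination visit to the closest visit or uses its date, so a patient with Weeks 4 and 8 plus a later termination visit can still qualify.

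**4. Size.** If a share f is excluded and declines g points more than those kept, the mean decline is understated by f × g. For f = 6% and g = 6 this is 0.36; for f = 10% and g = 6 it is 0.60. The documents give neither f nor g, so the following simulations rest on assumptions.

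*Certain withdrawal at a trigger.* Arms of 50, true mean -3.0, slope SD 4 per 24 weeks, residual SD 2, baseline as a time-zero response:

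| Observed drop that triggers withdrawal | All data | Three-value rule | Understatement |
|---|---|---|---|
| 5 points | -3.03 | -2.46 | 0.57 |
| 6 points | -3.03 | -2.69 | 0.34 |
| 8 points | – | – | 0.1 or less |
| 10 points | – | – | near zero |

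At 5 to 6 points the rule drops 4 to 7 of the 50 patients.

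*The same mechanism with change from baseline as the outcome and no time-zero value.* If the estimand is the slope, the understatement is only 0.03 to 0.14 for triggers of 5 to 8 points. If Week 24 is read as intercept plus slope, it is 0.68, 0.39 and 0.11 at 5, 6 and 8 points.

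*Withdrawal with 80% probability at the trigger.* Baseline as a time-zero response, slope SD 2.8 to 3.8, residual SD 1.7 to 2.5, 1% background dropout per visit, 2,000 arms per setting. The last column is the rejection rate of the one-sided 5% test against -4%:

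| True change | Trigger | All data | Rule | Shift | Excluded | Rejects: all / rule |
|---|---|---|---|---|---|---|
| -1.5 | 5 | -1.50 to -1.52 | -1.19 to -1.25 | 0.25 to 0.34 | 7% to 16% | – |
| -1.5 | 8 | -1.48 to -1.51 | -1.41 to -1.47 | 0.02 to 0.08 | 2% to 5% | – |
| -4.0 | 5 | -4.03 | -3.55 to -3.63 | 0.40 to 0.48 | 11% to 20% | 4–5% / 13–16% |
| -4.0 | 8 | -3.98 to -4.02 | -3.90 to -3.98 | 0.04 to 0.12 | 3% to 6% | 5–6% / 5–7% |
| -4.0 | none (5% random loss per visit) | -3.984 | -3.985 | 0.00 | 10% | 6% / 6% |

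**5. The sensitivity analyses.** SAP 8.1 gives early terminators other than deaths the average change of same-cohort patients with data at each visit. If a share f leaves and those still observed average m, the imputed mean is (1 - f) × m + f × m = m, so a faster decline is not restored. Only deaths receive a low value, 30% predicted. The SAP does not say whether the three-value rule also governs the run on the full analysis set (FAS).

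**6. Precision.** Losing 5 of 50 widens the half-width to 1.96 × 4.5 / √45 = 1.31.

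**The case against.** The strongest reply is that the size is not established. Protocol 5.6 leaves withdrawal to the investigator's judgement and sets no threshold, and dropout unrelated to FVC produces no bias. Even under a 5-point trigger, the effect nearly disappears if the estimand is the slope of change from baseline with no time-zero value. SAP 8.1 can be read that way. All of this stands, and it is why the size is given as a range that reaches almost to zero.

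The plan also contains more than the primary model: an FAS sensitivity analysis, a low imputed value for deaths, a second in-clinic FVC model with no stated minimum, and termination visits that can supply the third value. These soften the point. They do not remove it, because the single-arm comparisons are not tied to the second model and the imputation does not repair the selection.

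A reader might infer more than the documents support:
- *That decline is certainly understated, or by as much as 0.9 points.* A simulated mixture does give -3.32 with all data and -2.40 with the rule, but it assumes that 10% of patients lose 16 points in 24 weeks. Nothing in the documents supports that share.
- *That everyone who leaves before Week 12 vanishes.* SAP 6.4 makes this too broad.
- *That the comparison between arms is biased in a known direction.* The simulations are single-arm. The difference could move either way.
- *That the PP choice adds a known further bias.* Its effect was not isolated. PP is specified in the protocol, and two of its four listed exclusions (eligibility and consent) are not post-randomisation events.

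**Conclusion.** The concern holds in limited form. The identifiability rationale is wrong, and the SAP's other FVC models do not follow it. Where early loss is linked to FVC decline, the rule understates decline in the comparisons with -4% and the registries.

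The size depends on an unstated dropout rate and mechanism, and on how baseline enters the model. The understatement runs from near zero (dropout unrelated to FVC, or triggers of 8 to 10 points) to about 0.6 points with certain withdrawal at 5 points. It is slightly more if Week 24 is read as intercept plus slope of the change model. At its upper end it is about half the planned half-width of 1.25 (0.6 / 1.25 = 0.48).

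This should be fixed, but it does not undermine the study: the primary objective is safety and tolerability, and FVC is a secondary objective.

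**What to change.** - Delete the three-value rule and its rationale from SAP 8.1.
- Fit the primary mixed model to all randomised, treated patients with a baseline and at least one post-baseline FVC % predicted.
- Use baseline once, either as a time-zero response or as a covariate, and state how the Week 24 change is read from the model.
- Present this all-treated result at least beside the protocol-specified PP result, and use it for the -4% and registry comparisons.
- Report exclusions by arm and reason, including patients with no post-baseline value, whom the revised model still cannot use.
- Record the change in SAP section 12. State there that it follows the October 2020 review of preliminary dose-comparison data, so readers know it was made after data had been seen in an open-label study.

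The cost is revised SAP text, one further model run and that disclosure. The reported decline may look slightly worse.
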